13.4 Poolability Analysis

All investigational sites will follow the requirements of the study protocol and standardized data collection procedures. The primary evaluations will be presented separately for each site using descriptive statistics. Poolability of the primary evaluations across investigational sites will be evaluated using a regression model with fixed effects for site. Sites enrolling less than 5 subjects will be combined to form one-quasi site. If the p-value for the site effect is < 0.15, additional exploratory analyses will be performed to understand any variations in outcomes by site.

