2.2 Sample Size

Up to 10 sites in the US and EU are expected to participate in the study with 100 subjects enrolled. Each study site will be limited to 30% of total patient population.

The target population is comprised of subjects scheduled for embolization procedures with HydroPearl microspheres used on-label via radial access.

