3.2.1 Primary Evaluations

Primary Safety Evaluation:

The primary safety evaluation is freedom from major adverse events and radial access complications within 30 days post-procedure.

Major Adverse Events are defined as:

1. Death
2. MI
3. Stroke

Radial Access related complications are defined as:

1. Radial artery occlusion
2. Hand ischemia
3. Arteriovenous fistula
4. Pseudoaneurysm
5. Any complication requiring surgical and/or endovascular intervention within 30 days of index procedure.

Primary Efficacy Evaluation:

The primary efficacy evaluations are procedural success and technical success.

1. Procedural success is defined as completing the planned procedure without femoral access bailout.
2. Technical success is defined as delivery of HydroPearl to the target vessel and slowing the blood flow with microsphere embolization. Embolization may be confirmed clinically or radiologically at the discretion of the site investigator.

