13.2 General Considerations

Evaluations will be reported with descriptive statistics including 95% confidence intervals. Continuous endpoints will report the mean and standard error, median, min, and maximum values. Categorical endpoints will be summarized by proportion of each category. Time-to-event endpoints will be summarized via Kaplan-Meier survival analyses, along with median and associated 95% interval. The associated Kaplan-Meier curves will be displayed as appropriate.

Sub-group analyses include, but are not limited to:

- UFE treatment procedure
- Hypervascular benign and malignant liver treatment procedures
- AVM procedures
- PAE treatment procedure

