13.7 Analysis of Study Evaluations

Study success is defined as sample size enrolled with minimal missing data to allow for robust descriptive statistics. No formal hypothesis tests will be performed; endpoints will be summarized with descriptive statistics.

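### Does Section 13.4 need to name the overall site test behind the 0.15 poolability trigger?

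*Combined protocol and SAP*

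**What the plan says.** Section 13.4 of the combined protocol and SAP makes three provisions.

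- By-site results come first and are unconditional: "The primary evaluations will be presented separately for each site using descriptive statistics".
- A model is then fitted: "Poolability of the primary evaluations across investigational sites will be evaluated using a regression model with fixed effects for site". Sites with fewer than 5 subjects are merged into one.
- The p-value has one use: "If the p-value for the site effect is < 0.15, additional exploratory analyses will be performed".

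The link function, the overall test and the case of an evaluation with no failures are not mentioned, and no other section supplies them.

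The outcomes are binary. For example, in Section 3.2.1, "Procedural success is defined as completing the planned procedure without femoral access bailout". On layout, Section 2.2 says "Up to 10 sites in the US and EU are expected to participate in the study with 100 subjects enrolled" and "Each study site will be limited to 30% of total patient population". Section 13.2 adds that "Evaluations will be reported with descriptive statistics including 95% confidence intervals", and Section 13.7 that "No formal hypothesis tests will be performed; endpoints will be summarized with descriptive statistics".

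**The concern.** A numerical threshold looks like a decision rule, and a rule based on a p-value is incomplete until the test is named. With 100 subjects over as many as 10 sites and few failures, most sites may have none. In a logistic model the log odds of such a site diverge and so does their standard error. The site then adds almost nothing to a joint Wald statistic but still uses a degree of freedom.

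If that test were run, the report could show a poolability p-value near 1 beside a table with every failure at one site. The trigger would miss the pattern it is meant to flag. Even without Wald, the remaining tests can fall on opposite sides of 0.15 for the same data, so the choice of test could decide whether the follow-up analyses are prompted.

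**Working it through.** **Inputs.** 100 subjects, up to 10 sites and a 30% site cap (Section 2.2), so at least four sites. Failure rates of 1.6% to 4.6% come from Sections 1 and 13.1. They are single outcomes in other cohorts, not forecasts for the primary evaluations. Site layouts and poor-site rates are assumptions.

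**The plan's own figure.** Section 13.1 claims more than 80% probability of at least one event at 1.6%: 1 − (1 − 0.016)^100 = 0.8007. It reproduces. The chance of no failures at all is therefore 20% at 1.6%; the same formula gives 16% at 1.8% and 0.9% at 4.6%.

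**One table: ten sites of 10, failures (5, 0, …, 0).** Overall rate 0.05, so 0.5 failures are expected per site, with binomial variance 10 × 0.05 × 0.95 = 0.475.

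- Score: Σ(x − 0.5)²/0.475 = (4.5² + 9 × 0.5²)/0.475 = 47.37 on 9 df, p<0.00001.
- Likelihood ratio: 2[5 ln(5/0.5) + 5 ln(5/9.5) + 90 ln(10/9.5)] = 25.84 on 9 df, p=0.0022.
- Exact: 10 × C(10,5)/C(100,5) = 0.000033.
- Wald: W = Σw(b − b̄)², where b is the site log odds, w = x(n − x)/n and b̄ is the w-weighted mean. Zero-failure sites have w=0, so only one site counts, W=0 and p=1.00.
- Linear-model F: R² = 47.37/100 = 0.4737, so F = (0.4737/9)/(0.5263/90) = 9.0 on 9 and 90 df, far below 0.15.

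For (5, 1, 0, …, 0), W = (2.5 × 0.9/3.4) × (ln 9)² = 3.195 on 9 df, p=0.956, against likelihood ratio 0.0029.

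**The other tests can also differ.** For (2, 0, …, 0): likelihood ratio 9.60, p=0.384; score 18.37, p=0.031; F p=0.026; exact 10 × C(10,2)/C(100,2) = 0.0909.

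**Why F follows score.** The linear-model R² equals the score statistic divided by 100, so F is an increasing function of the score statistic. The two differ only in reference distribution.

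**Share of simulated trials with p<0.15** (20,000 per scenario, one poor site at 30% against 1.8% elsewhere):

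| Layout | Wald | LR | Exact | Score | F |
|---|---|---|---|---|---|
| Ten sites of 10 | 0.02% | 62% | 66% | 75% | 75% |
| Five sites of 20 | 15% | 96% | 92% | 94% | 94% |

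With four sites of 25, which the cap allows, Wald reaches 0.15 in about 35% of trials, and in about 56% when the other sites fail at 4.6%.

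**Score against likelihood ratio at a 4.6% background.**

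| Layout and poor site | LR | Score |
|---|---|---|
| Ten sites of 10, one at 30% | 56.5% | 56.0% |
| Five sites of 20, one at 15% | 48% | 34% |
| 30/15/15/10/10/10/5/5, 30-subject site at 30% | 88% | 77% |

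With no site effect at 4.6%, likelihood ratio crosses 0.15 in 17.6% of trials with five sites of 20, and score in about 15.3% with four sites of 25. Either can slightly exceed the nominal 15%.

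**The case for a change.** The best argument for a change is that it costs two sentences. A p-value used as a trigger should be defined before data are seen; otherwise the test could be picked to fire or not. The possible disagreement is not trivial: likelihood ratio, score and exact tests differ on crossing 0.15 in roughly 6% to 12% of no-effect trials, and in 15% to 25% when one site fails at 15% against 1.8%. A Wald p near 1 beside a lopsided table would also be contradictory reporting.

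Part of this stands. The omission is genuine, joint logistic Wald is a poor choice with many small sites, and naming a test would be tidy. But the Wald failure needs two choices the plan does not make: a logistic link, then a joint Wald test. Its near-total loss of sensitivity also belongs to many-site layouts and weakens with four or five larger sites. Selective choice of test has little to gain, because the by-site figures that would expose it are reported in any case. A rule for evaluations with no failures adds nothing, since no site test exists there.

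**Conclusion.** No change is needed. This is missing detail that an analyst would fill sensibly, and specifying it brings no material gain. The linear F reading already behaves like the score test. An analyst fitting a logistic model would see the separation and would not rely on a Wald p of 1.00. Mandating one test would be a preference: score does better for a poor small site at a 1.8% background, while likelihood ratio does better for a poor large site and in several layouts at 4.6%.

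The effect on the study's results is nil. Pooling does not depend on the p-value, by-site results and 95% confidence intervals are planned regardless, crossing 0.15 leads only to exploratory analyses, and no formal tests are planned.

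The firing rates rest on assumed layouts and on background rates that need not match the composite safety evaluation. The conclusion does not depend on them, because it follows from the limited use that Section 13.4 makes of the p-value. It would need revisiting only if pooling or a formal claim were made conditional on that p-value.

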13.5 Handling of Missing Data

All data will be collected when possible to limit the amount of missing data. Site study coordinators will work with the site principal investigator to collect accurate patient data. The number of missing data will be reported. Only observed cases will be considered.

13.6 Subject Disposition

Subjects who sign an informed consent form, but do not meet all protocol eligibility criteria (i.e., screening failure), will be excluded from the statistical analyses.

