3.2.2 Additional Evaluations

Additional evaluations include:

1. Incidence of Radial Artery Occlusion Complications at any time
 - a. Arteritis
 - b. Cellulitis
 - c. Ecchymosis
 - d. Pain at puncture site
 - e. Hematoma

2. Quality of Life and health economics
3. Post embolization syndrome
4. Procedural endpoints:
 - a. Blood loss
 - b. Patient radiation exposure
 - c. Contrast volume
 - d. Time to hemostasis
 - e. Total procedural time
 - f. Time to discharge
 - g. Operative time
5. Access endpoints:
 - a. Radial artery spasm,
 - b. Time to discharge
6. Closure endpoints
 - a. Time to hemostasis
 - b. Time to ambulation
7. Tumor type
8. Number and size of tumors / fibroids
9. Post embolization syndrome
10. UFE:
 - a. If post-op MRI is obtained per standard of care: Effectiveness of HydroPearl measured by MRI.
 - i. Infarction is characterized by complete (100%), 90-99%, 50-89%, or less than 50%.
 - ii. Uterine Volume
 - iii. Dominant Fibroid Volume
 - b. EQ-5D
 - c. UFS-QoL
 - d. Return to normal activities
 - e. Pain VAS
 - f. Symptoms including bleeding and bulk
 - g. Pregnancy intention and occurrence
11. PAE:
 - a. IPSS with Quality of Life

- b. EQ-5D
- c. Return to normal activities
- d. Pain VAS
- e. Qmax
- f. Prostate volume

12. Liver Tumor Embolization:

- a. Tumor response (mRECIST - CR, PR, SD, PD)
- b. EQ-5D
- c. Return to normal activities
- d. Pain VAS
- e. Disease stage

13. Other Hypervascular Tumors

- a. Infarction
- b. Tumor Response (mRECIST – CR, PR, SD, PD)
- c. Return to normal activities
- d. Pain VAS

14. Arteriovenous malformations:

- a. EQ-5D
- b. Return to normal activities
- c. Pain VAS

4 Study Design

This is a prospective, multi-center, registry study to assess the procedural success, technical success, and complication rate of radial access procedures using HydroPearl microspheres.

A subject is considered enrolled into the study once the guidewire is inserted into the radial artery.

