4.1.2 Exclusion Criteria

Subjects will not be permitted to participate in the study if they meet any of the following exclusion criteria:

1. Unable to have a procedure with radial access for any reason.
2. Participating in another clinical study which, in the opinion of the investigator, could impact the results of this registry.
3. Pregnant or planning to become pregnant during the study.

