5.5 Written Informed Consent

Written Informed Consent must be obtained prior to any study-related procedures*. The site principal investigator will ensure that proper informed consent is provided, including ensuring the subject is given full and adequate oral and written information about the nature, purpose, possible risks and benefits of the study. Subjects must also be notified that they are free to withdraw from the study at any time. The subject must be given the opportunity to ask questions and adequate time to consider the information provided. The site principal investigator will ensure that the subject has met all eligibility criteria prior to enrollment in the study.

The site principal investigator must store the original, signed written ICF per site specific procedures. A copy of the written ICF (paper or electronic) must be given to the subject. Any modifications made to the ICF must first be approved by the Sponsor and IRB/EC.

**Pre-procedure assessments considered standard of care completed prior to obtaining informed consent do not need to be repeated if performed within 90 days of the procedure unless the investigator feels it is medically necessary.*

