7.1 Screening/ Baseline Visit

Prior to the procedure, subjects must sign the informed consent form, meet all the inclusion and none of the exclusion criteria. The screening visit will follow each study site's standard of care and typically consists of a review of medical history and demographics, blood tests, imaging, review of concomitant medications, and pregnancy test if appropriate.

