13.3 Analysis Populations

Analyses for primary and secondary evaluations will be based on the Primary Analysis Set, defined as all enrolled subjects (i.e., those who signed the informed consent form and meet all protocol eligibility criteria) who are treated.

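### Sections 13.3 and 13.6 remove a treated subject found ineligible after the procedure from the primary safety and success rates, and no all-exposed set is defined

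*Combined protocol and SAP*

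**What the plan says.** Two statistical sections apply an eligibility condition to the analysis.

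- Section 13.3 defines one set, the Primary Analysis Set, for the primary and secondary evaluations: "all enrolled subjects (i.e., those who signed the informed consent form and meet all protocol eligibility criteria) who are treated".
- Section 13.6 says that subjects who sign the consent form but "do not meet all protocol eligibility criteria (i.e., screening failure), will be excluded from the statistical analyses".

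Neither section says by when the ineligibility must have been found, and no separate safety or all-exposed set is defined.

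Section 4 defines enrollment differently from the parenthesis in 13.3: "A subject is considered enrolled into the study once the guidewire is inserted into the radial artery".

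Other sections say when eligibility should be checked. Section 5.5: "The site principal investigator will ensure that the subject has met all eligibility criteria prior to enrollment in the study". Section 7.1: "Prior to the procedure, subjects must sign the informed consent form, meet all the inclusion and none of the exclusion criteria". Section 9.1 and both schedules of events also place the check at screening or baseline. Section 13.8 provides for a summary of protocol deviations.

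**The concern.** An eligibility check made before the procedure can be wrong, and the error can surface later. Source data verification takes place at periodic on-site visits (synopsis, Data Quality; Section 10), which may follow treatment. Participation in another study that bears on exclusion 2 may be undisclosed at screening. In such a case the subject has already been exposed to the device and the radial procedure. The literal effect of 13.3 and 13.6 is to take that subject out of the denominator and any event out of the numerator, for primary safety, procedural success and technical success alike.

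Sections 2.1 and 3.1 say that the registry is to describe safety, efficacy, success and complications in real-world use. There is no hypothesis test (Section 13.7), so the descriptive rates are the result. Removal after exposure makes those rates describe a cleaner group than the one treated. It also allows a decision on inclusion to be taken when the outcome is already known.

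**Working it through.** **1. Does the rule reach treated subjects?** Three situations, read against the text:

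| Situation | Section 13.3 | Section 13.6 |
|---|---|---|
| Consented, found ineligible before the procedure, not treated | Out | Out |
| Consented, eligible, treated | In | Not excluded |
| Consented, treated, found ineligible afterwards | Out (eligibility condition not met) | Out (no time limit) |

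The first row is an ordinary screening failure. The third row is the problem. Adopting the Section 4 meaning of enrolled does not by itself settle it, because the parenthesis in 13.3 and the sentence in 13.6 each impose the eligibility condition in their own words.

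**2. The plan's own figure.** Section 13.1 gives 100 evaluable patients, a 1.6% event rate and a probability above 80% of seeing at least one major complication.

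- Formula: P(at least one) = 1 − (1 − p)^n
- n = 100, p = 0.016: 1 − 0.984^100 = 0.8007, or 80.07%. The stated figure is reproduced.
- Smallest n for 80%: ln(0.2)/ln(0.984) = 99.8, so 100. There is no slack.
- n = 99: 1 − 0.984^99 = 0.7975 (79.7%)
- n = 98: 0.7942 (79.4%)
- n = 95: 0.7840 (78.4%)

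This assumes that exactly 100 subjects would otherwise be evaluable and that excluded subjects are not replaced.

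**3. Effect on a safety rate.** The documents give no count of treated but ineligible subjects. These scenarios are assumed, starting from 2 events in 100 treated subjects. Intervals are exact (Clopper-Pearson) 95%.

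| Subjects dropped | Reported event rate | 95% interval |
|---|---|---|
| None | 2/100 = 2.0% | 0.2 to 7.0% |
| One, with an event | 1/99 = 1.0% | 0.03 to 5.5% |
| Two, both with events | 0/98 = 0% | 0 to 3.7% |
| One, without an event | 2/99 = 2.0% | not computed |

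The last row shows that removal does not always flatter the result. With so few events, one removal can halve the rate or leave it practically unchanged, depending on which subject is removed.

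**The case against.** The strongest reply is that the protocol places eligibility before the procedure throughout, and that the term screening failure points to the screening visit. Section 13.6 may be meant only for people who never reach the procedure. That is a reasonable guess at intent, but those sections say when the check should happen. None says that a subject stays in the analysis if the check proves wrong after exposure.

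It is also fair to say that such cases are probably uncommon, since the criteria are few and broad, and that the intervals above overlap widely. This bears on size, not on whether the rule is right.

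Two stronger readings are tempting and are not supported:

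- **Femoral bailouts could be reclassified as ineligible.** Exclusion 1, "Unable to have a procedure with radial access for any reason", has no time point in its own sentence, so a reader might infer that a radial failure during the procedure makes the subject a screening failure. With 2 bailouts in 100, procedural success would then be 98/98 = 100% instead of 98/100 = 98%. The documents point the other way. Sections 5.5, 7.1 and 9.1 and the schedules put the check before the procedure, inclusion 2 turns on what is scheduled, and Section 3.2.1 reads "Procedural success is defined as completing the planned procedure without femoral access bailout". If bailout made a subject ineligible, that endpoint could never record one. The plan does not instruct such relabelling, and the 98% versus 100% contrast should not be used as the size of this point.
- **Events would be hidden.** Section 8.3 requires device related adverse events from enrollment onward to be reported on the eCRF, and 13.8 summarises deviations. Such events would leave the primary rates, not the study record.

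A pregnancy during follow-up is also a poor example of a late breach, because Section 3.2.2 collects pregnancy occurrence as an evaluation after UFE.

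**Conclusion.** The point holds in a limited form. As written, 13.3 and 13.6 exclude a treated subject whose ineligibility is found afterwards from every primary rate, and there is no all-exposed set in which that subject would count. This is a stated rule that works against the registry's aim, not merely a missing detail.

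Its size cannot be taken from the documents. Under the assumed scenario, one removal moves a 2.0% event rate to 1.0%. One removal from exactly 100 evaluable subjects also takes the Section 13.1 probability from 80.07% to 79.7%. That is a fall of about 0.3 percentage points, small in itself but enough to make the statement of more than 80% untrue. The conclusion rests on a literal reading of 13.3 and 13.6. If the sponsor already means to exclude only subjects found ineligible before the procedure, the amendment simply records that.

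**What to change.** 1. **Section 13.6:** limit screening failure to ineligibility identified before enrollment as Section 4 defines it, that is, before guidewire insertion.
2. **Section 13.3:** use the Section 4 definition of enrolled in place of the present parenthesis, and state that a subject is not removed from the Primary Analysis Set for ineligibility found after enrollment.
3. **Section 13.8:** report such breaches as protocol deviations, with one sensitivity summary of the primary evaluations that excludes the subjects concerned.
4. **Optional clarification:** state in exclusion 1, in both the synopsis and Section 4.1.2, that it is judged before the procedure. This agrees with Sections 5.5, 7.1 and 9.1 and leaves no doubt that a femoral bailout counts as a procedural failure.

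The change does not address radial punctures that fail before the guidewire is in, since Section 4 does not count those subjects as enrolled. It also leaves the treated condition in 13.3 as it stands.

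The cost is a wording amendment, with the notification to the IRB/EC that Section 5.3 requires, one extra table, and possibly slightly less favourable reported rates.

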13.7 Analysis of Study Evaluations

Study success is defined as sample size enrolled with minimal missing data to allow for robust descriptive statistics. No formal hypothesis tests will be performed; endpoints will be summarized with descriptive statistics.

13.8 Protocol Deviations

Deviations from the procedures outlined in the study protocol will be reported by study sites on eCRFs. Protocol deviations will be summarized for all deviations and by type with event counts and number of subjects with at least one deviation.

